## 1.0 Objectives

The overarching goal of this proposal is to understand the comparative effectiveness of obesity counseling as covered by Centers for Medicare and Medicaid Services (CMS) in improving weight loss for adults either with or at high risk of type 2 diabetes. CMS and most insurers now include obesity screening and counseling benefits, with no cost sharing to patients. Since overweight patients are at highest risk for diabetes, improved weight management services could prevent diabetes and its negative health outcomes. Beneficiaries with obesity are eligible for up to 20 face-to-face visits for weight counseling in the primary care setting. We propose comparing weight and diabetes outcomes in three states using electronic health record (HER) and claims data before and after this policy was implemented. The PaTH network brings together six academic health systems – the University of Pittsburgh/University of Pittsburgh Medical Center, Penn State College of Medicine/Hershey Medical Center, Temple University School of Medicine/Temple Health, and the Johns Hopkins University/Johns Hopkins Health System/Johns Hopkins Health Care, Geisinger Health Systems, and The University of Utah – to function as an integrated research network and learning health system, providing an infrastructure for observational studies, such as the one proposed here, that require populations beyond a single health system to answer important patient-centered health services questions ([www.pathnetwork.org](http://www.pathnetwork.org)). Using the PaTH Clinical Data Research Network (CDRN) infrastructure, we propose the following specific aims:

**Aim 1: Evaluate the impact of universal preventive service coverage for obesity screening and counseling on weight loss, diabetes incidence, and diabetes outcomes, in patients with diabetes or at high risk for diabetes (defined by body mass index (BMI)  $\geq 25$ ).** We will determine how the annual probability of receiving obesity and/or nutritional counseling (as defined by Current Procedural Terminology (CPT) code) changed pre- and post-policy across all insurers in a cohort of patients with diabetes and at high risk for diabetes. We hypothesize that individual patients are more likely to receive counseling following coverage implementation. Further, we hypothesize that patients who receive a greater number of face-to-face visits will have greater weight loss compared to those who receive fewer visits.

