**Aim 2: Compare patient weight loss and diabetes-related outcomes among those who receive obesity screening and counseling to those who do not, following implementation of preventive service coverage.** We will examine post-policy impact of obesity screening and counseling in a cohort of patients with diabetes and at high risk for diabetes. Specific outcomes to be examined include weight loss, diabetes incidence, and diabetes outcomes (including hemoglobin A1c, controlled blood pressure, use of a statin medication). Further, we will determine patient characteristics, including demographics (age, race/ethnicity, rurality), and practice characteristics, including provider type, and their impact on receiving/providing obesity screening and counseling. Understanding patient and practice characteristics most likely to engage in obesity counseling can identify best practices and inform how to increase engagement by both patients and providers.

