### **3.2 Exclusion Criteria**

- Patients under the age of 18

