### 7.2 Study Procedures

For the specific needs of this proposal, we will define 2 patient cohorts using the PaTH Network: (1) Diabetes cohort and (2) At-risk for diabetes cohort. As demonstrated in the table below, there are over 328,000 patients with a diagnosis of diabetes (defined as age 18 and older with a diagnosis of diabetes mellitus – ICD9 250.xx) and over 2 million patients at risk for diabetes (defined as age 18 and older with a BMI of  $\geq 25$ ) within the PaTH network.

Patient Characteristics	Penn State University (N=25,219)	University of Pittsburgh (N=150,589)	Johns Hopkins University (N=60,324)	Temple University (N=40,536)	University of Utah (N=51,787)	PaTH Total (N=328,455)
Patients with Diabetes						
Insurance type						
Private	9,874 (38%)	60,223 (40%)	32,371 (54%)	5,261 (13%)	21,264 (41%)	128,993 (39%)
Medicaid	1,890 (8%)	10,165 (7%)	727 (1%)	21,759 (54%)	4,189 (8%)	38,730 (12%)
Medicare	12,998 (52%)	54,675 (36%)	22,826 (38%)	10,916 (27%)	23,997 (46%)	125,412 (38%)
Uninsured	457 (2%)	11,625 (8%)	485 (1%)	2,599 (6%)	2,337 (5%)	17,503 (5%)
Race						
White	21,780 (86%)	116,056 (77%)	32,544 (54%)	14,347 (35%)	39,580 (76%)	224,307 (68%)
African-American	1,679 (7%)	15,336 (10%)	20,053 (33%)	14,656 (36%)	944 (2%)	52,668 (16%)
Other	1,760 (7%)	19,197 (13%)	7,727 (13%)	11,533 (29%)	11,263 (22%)	51,480 (16%)
Hispanic Ethnicity	1,054 (4%)	697 (0.5%)	2,002 (3%)	7,356 (18%)	6,077 (12%)	17,186 (5%)
Female Gender	12,014 (48%)	70,623 (47%)	30,912 (51%)	22,485 (55%)	25,727 (50%)	161,761 (49%)
Patients At-Risk for Diabetes						
	(N=167,799)	(N=950,020)	(N=471,860)	(N=212,314)	(N=260,506)	(N=2,062,499)
BMI						
25-29.9	69,353 (30%)	433,799 (31%)	226,113 (32%)	92,807 (31%)	122,583 (31%)	944,655 (32%)
30-34.9	48,353 (21%)	268,236 (19%)	128,799 (18%)	60,330 (20%)	87,023 (22%)	592,741 (20%)
35-39.9	25,388 (11%)	128,113 (9%)	58,072 (8%)	29,930 (10%)	70,774 (18%)	312,277 (10%)
40+	24,705 (11%)	94,550 (7%)	43,377 (6%)	23,321 (8%)	25,410 (7%)	211,363 (7%)

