***Diabetes Cohort Definition.*** During year 1 of the proposed project, the investigative team, in collaboration with the PaTH Network, will identify a valid cohort of patients with type 2 diabetes. The cohort of patients under study will be defined as all patients age 18 and older with an indication of type 2 diabetes during the proposed study time frame. Patients will be classified as having diabetes using a clinically validated algorithm: type 2 diabetes mellitus on the problem list, diabetes-specific medications, hemoglobin A1c (HbA1c) results > 7.0%, or one inpatient diagnosis code or two outpatient diagnosis codes for type 2 diabetes (ICD-9 codes 250.xx). The diabetes cohort will be further limited to patients who will likely be captured in the PaTH EHR records or claims data so that outcome assessments can occur. Thus, we will further limit the diabetes cohort to patients who have either: (1) had at least 2 outpatient primary care visits in one of the PaTH health systems in the past 3 years (since January 1, 2012), or (2) for whom claims data are available. The cohort will be dynamic, with new patients added into the cohort after 2015 as they meet the diabetes cohort definition prospectively. The observational period for the outcome variables will be for the 10-year period from 2009-2019, thus including 3 years of data prior to the first policy change (CMS instituting coverage for intensive behavioral therapy for obesity) and 3 years after the last policy change (Pennsylvania Medicaid expansion) under study.

Following the definition of the diabetes cohort and key diabetes outcomes and covariates as described above, an initial extraction of variables will be conducted in Year 2 of the proposed project for years 2009-2015. This early data extraction from the PaTH Network will allow for cohort validation and data cleaning and editing, as well as required programming and determination of the analysis models. We will utilize this initial data extraction in Years 2 and 3 to analyze the impact of early health policy changes, as well as to prepare a manuscript of both the protocol and early findings of policy impact. The final data extraction will occur during the final quarter of Year 4 of the proposed project, allowing for completion of a ten-year time period (2019).

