***At-risk Cohort Definition.*** The cohort of patients under study will be defined as patients age 18 and older who are at risk for the development of diabetes, based on being overweight. Patients seen at one of the four PaTH institutions will be included in the at-risk cohort if they have a  $BMI \geq 25 \text{ kg/m}^2$ , based on most recent recorded weight and at least one recorded height. The at-risk cohort will be further limited to patients who will likely to be captured in the PaTH EHR records or claims data so that outcome assessments can occur. Thus, we will further limit the at-risk cohort to patients who have either: (1) had at least 2 outpatient primary care visits in one of the PaTH health systems in the past 3 years (since January 1, 2012), or (2) for whom claims data is available. The cohort will be dynamic, with new patients added into the cohort after 2015 as they meet the at-risk cohort definition prospectively. Patients will not be removed from the cohort, even if they are no longer overweight. The observational period for the outcome variables will be for the 10-year period from 2009-2019, thus including 3 years of data prior to the first policy change (CMS instituting coverage for intensive behavioral therapy for obesity) and 3 years after the last policy change (Pennsylvania Medicaid expansion) under study.

[figure not shown]
intensive behavioral therapy for obesity) and 3 years after the last policy change (Pennsylvania Medicaid expansion) under study.

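### Aim 2 and the visit-count models compare counseled with uncounseled patients in cohorts wider than the population offered the obesity benefit, and BMI is not named in the adjustment, so the contrast partly reflects BMI band

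*Combined protocol and SAP*

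**What the plan says.** **The benefit.** Section 1.0 states: "Beneficiaries with obesity are eligible for up to 20 face-to-face visits for weight counseling in the primary care setting". No BMI cut-off for obesity is given.

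**The contrast.** Aim 2 is to "Compare patient weight loss and diabetes-related outcomes among those who receive obesity screening and counseling to those who do not" once coverage is in place. Its population is the two study cohorts: "We will examine post-policy impact of obesity screening and counseling in a cohort of patients with diabetes and at high risk for diabetes". Section 8.0 then uses the amount of screening and counseling as a predictor in post-policy mixed models for weight loss, diabetes incidence and diabetes outcomes.

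**The cohorts.** At-risk entry requires BMI of at least 25, "based on most recent recorded weight and at least one recorded height" (section 7.2). After entry, "Patients will not be removed from the cohort, even if they are no longer overweight". For diabetes, "The cohort of patients under study will be defined as all patients age 18 and older with an indication of type 2 diabetes" in the study period, with a further condition on primary care visits or claims but none on BMI. The only exclusion in section 3.2 is "Patients under the age of 18".

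**Adjustment.** Table 1 lists individual-level exposures as sociodemographics, with examples, and co-morbidities. The propensity score paragraph lists demographics, insurance, co-morbidities, health behaviors and service use. The subgroups concern insurance, new enrollment, gender, age and race-ethnicity. None of the three names BMI, baseline weight or eligibility for the benefit.

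**The concern.** The uncounseled group combines two kinds of patient: those with obesity who were offered covered visits and did not have them, and those below the obesity threshold to whom the covered visits do not apply. Only the first kind is a natural comparator for counseled patients. The second kind is lighter by definition and may have a different weight course and diabetes risk for reasons unrelated to counseling.

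If the two are pooled without conditioning on BMI, the Aim 2 difference mixes the counseling effect with a difference between BMI bands. The slope on visit count is exposed to the same mixing, because the extra patients sit mainly at zero visits. The result would also describe a population wider than the one the benefit serves. Section 8.0 itself expects to detect very small effects, so even a modest distortion could appear as a significant finding.

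**Working it through.** **1. Check the plan's counts** (patient characteristics table, section 7.2).
- BMI 25-29.9 over the five sites: 69,353 + 433,799 + 226,113 + 92,807 + 122,583 = 944,655, as printed.
- All four bands: 944,655 + 592,741 + 312,277 + 211,363 = 2,061,036. The printed at-risk N is 2,062,499, a difference of 1,463.
- The printed 32% for BMI 25-29.9 does not reproduce on the at-risk N: 944,655 / 2,062,499 = 45.8%. It implies a denominator of 944,655 / 0.32, about 2.95 million, which the table does not show.
- Bands minus site N: Penn State 0, Pittsburgh -25,322, Johns Hopkins -15,499, Temple -5,926, Utah +45,284.

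**2. Share below BMI 30** (cut-off assumed; it is also a band boundary in the table).
- Of patients with a band: 944,655 / 2,061,036 = 45.8%.
- Without Utah: (944,655 - 122,583) / (2,061,036 - 305,790) = 822,072 / 1,755,246 = 46.8%.
- By site, on site N: 41% to 48%. The table's inconsistencies do not change the picture.
- BMI 30 or more: 592,741 + 312,277 + 211,363 = 1,116,381, or 54.1% of 2,062,499.

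**3. Share of the zero-visit group.** Let I = 944,655, E = 1,116,381, and u = uptake among patients at BMI 30 or more. The documents give no uptake, so u is assumed. If nobody below BMI 30 has a counted visit, the share is s = I / (I + E(1 - u)). At u = 5%: 944,655 / (944,655 + 1,060,562) = 47.1%.

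| u | s |
|---|---|
| 0.5% | 46.0% |
| 1% | 46.1% |
| 5% | 47.1% |
| 10% | 48.5% |
| 20% | 51.4% |

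**4. Effect on an unadjusted contrast.** Let d be the difference in mean uncounseled weight change between patients below and above BMI 30. With no counseling effect, counseled patients have the upper-band mean, and uncounseled patients have that mean shifted by s × d. The contrast is therefore off by s × d, which is 0.46d to 0.51d over the table.

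**5. Allow for nutritional counseling or screening codes below BMI 30.** Let these patients have counted visits at v times the rate of patients at BMI 30 or more. They then also appear in the counseled group, and the shift is d times the difference between the two shares. At u = 1%:
- v = 0.25: 0.460 - 0.175 = 0.285, so 0.29d.
- v = 0.5: 0.460 - 0.297 = 0.163, so 0.16d.
- v = 1: 0.458 - 0.458 = 0.

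The 0.46 multiplier therefore holds only if few patients below BMI 30 are counted as counseled.

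**6. Precision after restriction.** The detectable difference in SD units is (1.96 + 0.84) × sqrt(1/n1 + 1/n0), assuming two-sided 5%, 80% power and independent observations. At u = 5%, n1 = 55,819. With n0 = 1,060,562 (restricted) it is 0.0122; with n0 = 2,005,217 (unrestricted) it is 0.0120. At u = 1% both are 0.0266. The number of counseled patients limits precision, so restriction costs almost none.

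**The case against.** The strongest reply is that the plan does not fix the analysis in the way the concern supposes. Four parts of it stand.

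- **Exposure.** A reader might infer that patients below BMI 30 cannot have a counted visit. The documents do not say so. Aim 1 counts nutritional as well as obesity counseling by CPT code across insurers, section 8.0 counts screening too, and nothing confines those services to obesity. BMI 30 is itself an assumption.
- **Share.** A reader might take 46% as the ineligible share of the analyzed zero-visit group. The table's counts precede the restriction to patients with two primary care visits or claims data. If they follow the cohort definition, they also rest on the latest weight, which need not reflect status when counseling was available. No BMI data are given for the diabetes cohort, so no share can be computed there.
- **Size.** Assuming d of 0.5 to 1.0 kg per year would give 0.23 to 0.46 kg per year, but no document supplies d. That would also be a crude contrast, whereas the plan uses covariate-adjusted mixed models with subject-specific intercepts and slopes.
- **Adjustment.** It is tempting to say that adjustment must extrapolate because patients below the threshold have no counseled counterparts. That goes too far. The effect among counseled patients needs uncounseled patients of similar BMI, and these should exist among the roughly 1.1 million at BMI 30 or more. The covariate and propensity wording is open, so BMI could still be included.

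Entry at BMI 25 is also a deliberate choice, explicit in Aim 1. None of this supplies a commitment to condition on BMI or eligibility in the Aim 2 contrast, and that is the gap.

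**Conclusion.** The mismatch between the population offered the benefit and the populations analyzed is in the text. As written, the Aim 2 contrast and the visit-count models can mix the counseling effect with differences between BMI bands, because nothing restricts the comparators or names BMI in the adjustment. This should be corrected before the analysis.

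The amount of bias cannot be computed from the documents. What can be said is that about 46% of the at-risk counts with a BMI band lie below BMI 30. An unadjusted contrast would then shift by roughly 0.46 times the BMI-band difference in uncounseled weight change. This rests on the BMI 30 reading of obesity, on the unrestricted table counts, and on few patients below BMI 30 being counseled. No multiplier was derived for the visit-count slope or for the diabetes cohort.

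**What to change.** In section 8.0:

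1. Run the main Aim 2 contrast and the visit-count models, in both cohorts, in patients who meet the obesity criterion (BMI of at least 30, to be stated in the plan) on the last weight before a defined index date. The most recent weight used for cohort entry is not suitable, since it may follow counseling.
2. Define how uncounseled patients receive an index date. Table 1 measures weight loss between first and final IBT visits and diabetes incidence after counseling, so neither is defined for patients with no visits.
3. Include index BMI in the outcome model and the propensity score.
4. List the codes that count as exposure, so that covered visits can be told apart from nutritional counseling and screening.
5. Report patients below BMI 30 separately, and keep the BMI 25 cohort for Aim 1 and description.

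The cost is a smaller and narrower analysis population: 1,116,381 patients, about 54% of the at-risk counts, before the visit or claims restriction, whose effect is not given. Assigning comparator index dates is real work. The heights and weights are already part of the planned data, and the loss of precision is negligible under the assumptions shown.

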## 2.0 Background

### 2.1 Scientific Background and Gaps

Overweight and obesity are America's number one health concern. The prevalence of obesity in the US is greater than 36%, which is far above the Healthy People 2020 objective of less than 30.5%. Perhaps most concerning is the rate that obesity has increased, having doubled since 1970. As the second most preventable cause of death, obesity is a risk factor for diabetes, cardiovascular disease, stroke, and cancer, all major causes of death in the US. Addressing obesity through lifestyle interventions decreases the risk of developing type 2 diabetes, a disease which affects over 29 million people (9.3% of the US population). Diabetes is associated with serious complications, including cardiovascular disease, blindness, renal failure and lower extremity amputation. Although complications are preventable with proper medical and lifestyle management, including weight loss, nearly half of patients with diabetes do not have adequate glycemic control.

Primary care clinics may be an ideal setting for weight control interventions. Greater than 80% of Americans see a PCP regularly and access to primary care is expected to increase with health care reform. Further, as PCPs identify and treat the multitude of conditions affected by being overweight, including diabetes, they are ideally positioned to best engage their patients in weight management. The Centers for Medicare and Medicaid Services (CMS) implemented a healthcare procedure coding system code for intensive behavioral therapy (IBT) for obesity within primary care settings in 2012 to facilitate payment for addressing obesity, which was followed by universal coverage by insurers for IBT for adults of all ages in 2013. However, the impact of this coverage on patient-centered outcomes is largely unknown.

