**Table 1. Proposed Outcomes for the Pre-diabetes and Diabetes Cohorts**

Outcomes	Definition	Notes
Pre-diabetes cohort		
Weight loss during counseling	Weight lost from first IBT visit to final IBT visit	Available at all PaTH sites
Weight loss maintenance	% of weight lost during program and maintained over remaining time period, reported by year	Available at all PaTH sites
Diabetes incidence	% of patients who develop diabetes per year following weight counseling	Available at all PaTH sites
Patient-reported outcomes	-SF-12 -PHQ-2, PHQ-8, PHQ-9 -Physical function -sleep -fruit and vegetable consumption -social support -physical activity -PROMIS (PROMIS 29, physical function, depression) -healthy lifestyles -patient reported medication reconciliation	Available at some sites – Formal inventory of PROs will be collected at each institution at the beginning of the project, to be included as secondary outcomes
Diabetes cohort		
Weight loss during counseling	Weight lost from first IBT visit to final IBT visit	Available at all PaTH sites
Weight loss maintenance	% of weight lost during program and maintained over remaining time period, reported by year	Available at all PaTH sites
Patient reported outcomes	-SF-12 -PHQ-2, PHQ-8, PHQ-9 -Physical function -sleep -fruit and vegetable consumption -social support -physical activity -PROMIS (PROMIS 29, physical function, depression) -healthy lifestyles -patient reported medication reconciliation	Available at some sites – Formal inventory of PROs will be collected at each institution at the beginning of the project, to be included as secondary outcomes
Uncontrolled diabetes	Average A1c > 9 or no A1c	Available at all PaTH sites
Controlled blood pressure	SBP < 140, DBP < 90, averaged across values over year	Available at all PaTH sites
On a statin medication	Evidence of a statin medication on current EHR medication list	Available at all PaTH sites
Receiving annual eye exam	Documentation of eye exam once in past year	Available at all PaTH sites
Receiving annual urinary microalbumin test	Documentation of lab testing for urinary microalbumin at least once in past year	Available at all PaTH sites
Lower extremity amputations	Documentation of procedure for lower extremity amputation or billing code through health plans in past year	Available at all PaTH sites

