## 8.0 Statistical Plan

Descriptive statistics will be generated to describe the characteristics of different cohorts of interest. The diabetes related outcomes will be summarized at the individual level on a yearly basis. There will be binary outcomes (Yes/No) such as controlled diabetes, controlled blood pressures, receiving annual eye exam, receiving obesity and/or nutritional counseling, and count outcomes such as numbers of clinic visits, emergency department visits and hospitalization, and continuous outcomes such as cost of healthcare utilizations. The distributions of outcome measures will be examined by using minima, maxima, ranges, medians, quartiles, means, and standard deviations for continuous variables, and frequency and contingency tables for categorical variables.

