To evaluate the impact of policy changes on these outcomes, we will examine how these outcomes change over time, in response to the policy changes. As descriptive analyses, we will plot the mean trajectory of each yearly outcome at clinic level, health system level and state level. The statistical modeling of patterns of changes in individual level outcomes will be carried out through multi-level mixed-effects models. The mixed-effects model is a common and popular modeling technique for longitudinal data. A mixed-effects model can accommodate within- and between-subjects variability, as well as serial correlations. In addition, it has the flexibility to incorporate time-dependent covariates, incomplete data, and heteroscedasticity of the variances and correlations. The mixed-effects model will be specified in a multi-level fashion so that different levels of variability (e.g., individual characteristics, social environment, built environment) can be taken into account. The pattern of changes in the outcome will be assessed for pre- and post-periods, respectively, based on the piecewise/segmented regression models. The slope of each segment indicates the trend of change in diabetes outcome in that period. Therefore, the change in the trend/slope post-policy implementation may reveal the actual impact of the new policy controlling for baseline level and trend. Such modeling strategies share the same spirit of interrupted time series analysis. While the classical interrupted time series design often generates a single long series of data, we have a large number of short series from each individual subject, namely, longitudinal data. Depending on the types of the outcomes, we will specify mixed-effects models based on logistic

regression for a binary outcome, Poisson regression for a count outcome and linear regression for a continuous outcome as detailed below.

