In the multi-level modeling, the first-level unit is the yearly measurement for the individual subject (pre- and post-policy), the second-level unit is the individual subject, the third-level unit is the health system or clinic within the health system (cluster), and the fourth-level unit is the state. We set year 2014 as time origin for Utah when considering the policy impact of the ACA. Let  $Y_{ijkt}$  denote the binary response of having controlled diabetes at year  $t$  since policy changes for the  $k^{\text{th}}$  subject within the  $j^{\text{th}}$  cluster of the  $i^{\text{th}}$  state,  $t = -5, -4, \dots, 0, 1, \dots, 5$ ,  $i = 1, 2, 3$ ;  $j = 1, 2, \dots, c_i$ , and  $k = 1, 2, \dots, n_{ij}$ , where  $c_i$  is the number of clusters within the  $i^{\text{th}}$  state and  $n_{ij}$  is the sample size within the  $j^{\text{th}}$  cluster of the  $i^{\text{th}}$  state. An individual subject may not be in the system for all 11 timepoints of measurement, so  $t$  will have a smaller range of values for that individual subject. Also due to the different timeline of policy changes, the number of years before and after policy changes may vary. The probability of having controlled diabetes,  $\mu_{ijkt} = E(Y_{ijkt}) = \Pr[Y_{ijkt} = 1]$ , can be described by the following segmented logistic regression model

$$\begin{aligned} \text{logit } \mu_{ijkt} &= \log \{\Pr[Y_{ijkt} = 1] / \Pr[Y_{ijkt} = 0]\} \\ &= \beta_{0ijk} + (t + 5) \beta_{1ijk} && \text{if } -5 \leq t \leq 0, \text{ pre-period before policy changes} \\ &= \beta_{0ijk} + 5 \beta_{1ijk} + t \beta_{2ijk} && \text{if } 0 \leq t \leq 5, \text{ post-period after policy changes} \end{aligned}$$

where  $\beta_{mijk}$  ( $m = 0, 1, 2$ ) are subject-specific regression parameters, with  $\beta_{0ijk}$  being the log odds of having controlled diabetes at  $t = -5$ , and  $\beta_{1ijk}$  and  $\beta_{2ijk}$  being the slopes (annual change in log odds) for the pre- and post-periods, respectively. In the framework of a mixed-effects model, each  $\beta_{mijk}$  is modeled by

$$\beta_{mijk} = \mathbf{x}_{mijk}^T \boldsymbol{\beta}_m + \mathbf{z}_{ij}^T \boldsymbol{\gamma}_{1ij} + \boldsymbol{\gamma}_{2mijk}$$

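### Aim 2 names hemoglobin A1c as an outcome, but the plan defines only a yes/no indicator at average A1c above 9 (or no A1c) and never states the scale on which A1c is analysed

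*Combined protocol and SAP*

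**What the plan says.** Section 1.0, Aim 2, names as outcomes weight loss, diabetes incidence and "diabetes outcomes (including hemoglobin A1c, controlled blood pressure, use of a statin medication"). The paragraph of Section 8.0 on the post-policy effect of counseling repeats this list and says that models similar to those already described will be used. Neither place says whether A1c is a value or a category, which A1c summary is used, or what happens in a year without a test.

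Table 1 in Section 7.2 has one A1c-based row for the diabetes cohort, uncontrolled diabetes, defined as "Average A1c > 9 or no A1c". It has no row for the A1c value.

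Section 8.0 names "binary outcomes (Yes/No) such as controlled diabetes, controlled blood pressures, receiving annual eye exam" and, on the continuous side, "continuous outcomes such as cost of healthcare utilizations". The model written out in full is a segmented logistic mixed model whose response is said to "denote the binary response of having controlled diabetes at year" t. The same section provides for "linear regression for a continuous outcome as detailed below", in general terms. Its part on population-level analyses gives a similar outcome list with diabetes control standing where Aim 2 has hemoglobin A1c.

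**The concern.** A named outcome of Aim 2 has no definition that matches its name, and the nearest definition measures something else. Under the Table 1 row, a patient contributes to a glycemic effect only by moving across 9 or by changing from untested to tested. One of the ways into the diabetes cohort (Section 3.1) is an HbA1c above 7.0%, so a patient may enter at 8.5% and never count as uncontrolled in a year with a test.

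Two things are at stake. The first is the estimand: an effect on the probability of crossing 9 is not an effect on A1c, and sample size does not turn one into the other. The second is precision, in analyses where the counseled group or a subgroup is small. There is also room for a choice made after seeing data, because Section 7.2 places determination of the analysis models after the early data extraction and the A1c scale is open.

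**Working it through.** **What the plan's figures allow.** The documents give no power calculation, A1c mean, SD, share above 9, share untested, or share counseled. The one figure to reproduce is the diabetes cohort total in Section 7.2: 25,219 + 150,589 + 60,324 + 40,536 + 51,787 = 328,455, which agrees. Everything below that uses a distribution is an assumption.

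**Step 1, no assumption needed.** Under the Table 1 indicator, with a test in both years:

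| Yearly average A1c | Indicator before | Indicator after | Scored change |
|---|---|---|---|
| 8.5 to 7.2 | not above 9 | not above 9 | none |
| 11 to 9.5 | above 9 | above 9 | none |

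**Step 2, how many patients a shift moves across 9.** Assume A1c is normal with mean m and SD s. A fall of d in every patient moves a share Φ((9 + d − m)/s) − Φ((9 − m)/s) across the cut. For d = 0.5:
- m = 7.0, s = 1.5: 4.3%
- m = 7.5, s = 1.5: 6.7%
- m = 7.5, s = 1.8: 6.9%

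**Step 3, information kept by the cut.** For a normal outcome and a small mean shift, the efficiency of the indicator relative to the mean is φ(z)² / [p(1 − p)], where p is the share above 9 and z the matching normal quantile. For p = 0.10, z = 1.282 and φ(z) = 0.1755, giving 0.0308/0.09 = 0.342.

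| Share above 9 (assumed) | Kept | Lost |
|---|---|---|
| 5% | 0.224 | 78% |
| 10% | 0.342 | 66% |
| 15% | 0.426 | 57% |
| 20% | 0.490 | 51% |
| 30% | 0.576 | 42% |
| 50% | 0.637 | 36% |

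Cross-check by sample size for a 0.1 SD shift (two-sided 0.05, 80% power, both assumed): 1,570 per group for the mean, against 4,838, 3,840 and 3,315 for the indicator at p = 10%, 15% and 20%. The losses, 1 − 1,570/n, are 68%, 59% and 53%.

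**Step 4, adding untested patients.** Step 3 covers tested patients only. If a share q is untested and scored uncontrolled, and testing is unrelated to counseling, then P = q + (1 − q)p and the efficiency against mean A1c in those tested is (1 − q)φ(z)² / [P(1 − P)]. For q = 10% to 30% and p = 10% to 20%, the loss is 65% to 91%.

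**Step 5, does it matter for power?** Over the whole cohort, 328,455 × 0.342 is about 112,000 and 328,455 × 0.490 about 161,000 effective patients, still very large. For counseled against uncounseled patients, assume a 0.1-point difference, SD 1.5, two-sided 0.05 and independent patients:

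| Share counseled (assumed) | Power, mean A1c | Power, indicator (p = 10% to 20%) |
|---|---|---|
| 0.5% | 77% | 32% to 45% |
| 1% | 97% | 57% to 74% |
| 5% | about 100% | about 100% |

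**The case against.** The strongest reply is that a continuous analysis may well be intended. The Aim 2 analysis paragraph lists hemoglobin A1c by name, in a list where blood pressure appears already dichotomised and A1c does not. Section 8.0 supplies a linear mixed model, its lists of binary and continuous outcomes are examples rather than inventories, and the logistic model is a worked case that is then extended to other outcome types. This stands. A reader might infer that A1c will be modelled only as a cut at 9, and the documents do not support that. They support the narrower statement that the scale is unstated and the only definition given is binary. The population-level list, with diabetes control in the place of A1c, leans towards the binary reading but does not settle it.

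A reader might also take a loss of half to two thirds as a property of this trial. It is not: it requires an assumed 10% to 20% above 9, roughly normal values, a uniform shift, tested patients only and independent observations. The planned model has repeated yearly measures and subject-specific slopes, so the ratio does not carry over exactly.

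Nor do the documents show that the trial is underpowered. Section 8.0 relies on very large numbers, counseling uptake is not given, and at 5% counseled both analyses have nearly full power in the example above.

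Finally, the background says that "nearly half of patients with diabetes do not have adequate glycemic control", and one might conclude that a cut at 9 misses that problem. The background gives no threshold for adequate control, so this cannot be settled here. Controlled diabetes is likewise never defined. Reading it as the complement of the Table 1 row is natural, but it is an inference.

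**Conclusion.** The point holds as a mismatch between a named outcome and its definition. Aim 2 and its analysis paragraph name A1c, while Table 1 and the written-out model deal with a yes/no indicator. If that indicator is what is analysed, changes on one side of 9 go unseen and the counseling effect on A1c is not estimated. That part needs no distributional assumption.

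The information loss is conditional: about 51% to 66% if 10% to 20% of tested patients exceed 9, and 36% to 78% over 50% down to 5%. It bears on power mainly if the counseled group or a subgroup is small, around 1% of the cohort in the example, which is itself an assumption. The main harm is to what is estimated, and the loss of precision is secondary.

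Because a missing A1c counts as uncontrolled, the indicator can also improve through more testing alone, with no change in A1c. That is a further reason to separate its components.

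**What to change.** 1. Add a row to Table 1 for the diabetes cohort: annual mean A1c, continuous, among patients tested that year, as the A1c outcome of Aim 2.
2. State in the Aim 2 analysis paragraph of Section 8.0 that this outcome uses the linear mixed-effects model already described there.
3. Keep the indicator as a secondary measure, label it by its threshold rather than as controlled diabetes, and report A1c above 9 and no A1c separately.
4. Report the proportion tested each year by counseling status.

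The cost is wording in Table 1 and Section 8.0. The A1c values are already needed to form the yearly average, and the model is already in the plan. There are two downsides. One more outcome is reported. The continuous outcome is also conditional on being tested, which may depend on counseling visits, so it can carry a selection effect. Item 4 lets a reader judge how serious that is, but does not remove it.
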